**The overarching hypothesis of this proposal is that aberrant brain responses to visceral pain signals within the homeostatic afferent processing network (HAPN) represent the primary mechanism responsible for bowel pain experiences in a subset of IBS patients (IBS-HAPN).** Our preliminary data has identified a pattern of brain activation differences within the HAPN following visceral stimulation in IBS subjects compared to healthy controls. Using fMRI, I will further characterize the HAPN pain responses of IBS-S subjects to additional non-visceral stimuli and following antidepressant therapy. I predict that this protocol will reveal a pattern of increased HAPN pain activations to both visceral and somatic stimuli—activations that are refractory to antidepressant pharmacotherapy. Ultimately these findings will demonstrate the mechanistic importance of the HAPN to pain experiences in the IBS-S subgroup.

*These goals will be realized through the pursuit of the following Specific Aims:*

**Specific Aim 1. To compare HAPN activations following noxious somatic stimulation in IBS subjects based on the presence of somatization.**

*Hypothesis 1:* As a result of a generalized abnormal pain response within the HAPN, IBS-S subjects will demonstrate greater HAPN activations with noxious somatic stimuli, compared to IBS subjects with no somatization and healthy controls.

**Specific Aim 2. To compare the effects of antidepressant therapy HAPN activations following noxious visceral stimulation in IBS subjects based on the presence of somatization.**

*Hypothesis 2:* Consistent with clinical refractoriness to antidepressant treatment, IBS-S subjects will demonstrate a persistent pattern of abnormal HAPN visceral activations following desipramine therapy, whereas significant improvements in HAPN visceral activations will be observed in IBS subjects with no somatization following antidepressant therapy.

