Analysis/interpretation: *Consistent with the clinical refractoriness to antidepressant therapy observed in IBS-S subjects, it is hypothesized that IBS-S subjects will exhibit a persistent pattern of abnormal HAPN activations in response to visceral stimulation following desipramine therapy.* By comparison, it is hypothesized that the IBS-No S group will exhibit decreases in HAPN activations in the post-treatment fMRI protocol (Figure 10, below). Region of interest two-way ANOVA models will be developed in comparing  $\Delta$ baseline-DES activations, with IBS Group (IBS-S and IBS-No S) as a between-subject factor. If the stated hypothesis is supported by the fMRI findings, it would suggest that the persistent HAPN activations in response to visceral afferent signals may result in the less robust clinical responses to desipramine therapy in the IBS-S. This finding would be an important addition to the existing literature, providing both insight into the central mechanisms involved in IBS antidepressant response, and also into the specific relevance of HAPN pain responses to the IBS-S subgroup.

Conversely, should HAPN activations be found to improve in both IBS groups following desipramine therapy, the possibility that HAPN visceral activations are indeed partially refractory to desipramine in IBS-S, but the detected between-group differences (IBS-S vs. IBS-No S) in post-desipramine changes in HAPN activation were smaller than expected, and thus not statistically significant. If this were the case, the ANOVA analyses would be likely demonstrate statistical trends between the IBS groups, and enrollment of additional subjects would be considered if feasible following power calculations. This additional step might lead to findings which allow for rejection of the null hypothesis.

[figure not shown]

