**B. Sample size calculations.** The power calculations performed to assess the adequacy of the proposed sample size are based on the preliminary data, and are driven by the hypotheses proposed in Aim 2. These calculations assumed accrual of all subjects prior to the 10-week interval, a 10% attrition rate in each arm (2 subjects per group) over the course of the trial, observed group mean differences in blood flow within the anterior cingulate cortex from the IBS subjects studied in the Preliminary Studies section, and the previously reported post-desipramine reductions in ACC activations (effect size = 0.33). With the proposed sample size (n=20 per group), the anticipated 2-way ANOVA design examining the fMRI data with one between-subjects factor (Group) would be powered at 0.95 for detecting the anticipated difference using a conservative treatment effect size of 0.33, while assessment of Group x Treatment effect would be powered at 0.82 (figure 12). This sample size would allow the detection of a desipramine effect size of 0.25 at  $p<0.01$ , and also permit the interpretation of predicted non-significant interactions as consistent with the stated hypotheses. These power calculations were conducted using SamplePower v2.0 (SPSS, Inc).

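### Aim 2's test compares change between groups and cannot show that activation in IBS-S persisted; no estimate or bound on the IBS-S change is planned

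*Combined protocol and SAP*

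**What the plan says.** Section A, Hypothesis 2, makes a claim about each group: "IBS-S subjects will demonstrate a persistent pattern of abnormal HAPN visceral activations following desipramine therapy, whereas significant improvements in HAPN visceral activations", the second half referring to IBS-No S. The same section predicts "activations that are refractory to antidepressant pharmacotherapy".

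Specific Aim 2, Analysis/interpretation, plans region-of-interest ANOVA models of the change from baseline to desipramine, with IBS Group as the between-subject factor. If the hypothesis is supported, "it would suggest that the persistent HAPN activations in response to visceral afferent signals may result in the less robust clinical responses to desipramine therapy". The contrasting case is that both groups improve and the group difference is too small to reach significance. Partial refractoriness in IBS-S then stays open, and more enrolment is considered.

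The Design and Methods paragraph of Aim 2 names the between-group difference after treatment as the primary endpoint. Sample size calculations assume "a 10% attrition rate in each arm (2 subjects per group) over the course of the trial" and give the power: "while assessment of Group x Treatment effect would be powered at 0.82". The same paragraph adds that the sample size allows predicted interactions that turn out non-significant to be taken as agreeing with the hypotheses.

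Neither Aim 2 nor the Data Analysis section gives a confidence interval, a margin or a numerical definition of 'persistent' for the IBS-S change.

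**The concern.** The hypothesis says something about IBS-S on its own: its abnormal activation persists under treatment. The test asks something else, whether the two groups' changes are equal. A significant result follows equally well from no fall in IBS-S and from a material fall in IBS-S with a larger one in IBS-No S. Only the first fits 'persistent' or 'refractory' in its ordinary sense.

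The sentence on non-significant interactions adds to the problem. With samples this small, non-significance is weak evidence of no effect, and the plan sets no precision requirement before it may count as support.

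At stake is the mechanistic conclusion of Aim 2. A real but smaller effect of desipramine on IBS-S activation could be described as central refractoriness, when the data support only a smaller reduction than in IBS-No S.

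**Working it through.** **Inputs from the documents.** 20 per group less 2 for attrition gives 18 completers per group (Sample size calculations). The planning effect size is 0.33, with no metric or SD stated. Stated power for Group x Treatment is 0.82.

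**Assumptions, not in the documents.** Two-sided alpha 0.05; effects in SD units of the change score, with equal SD in both groups; normal data.

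**The plan's own figure.** It can be matched only by assumption. Reading 0.33 as Cohen's f, with 40 subjects, 2 scans and pre-post correlation 0, the noncentrality is 0.33² × 40 × 2 = 8.71. On 1 and 38 df, power is 0.820, which agrees with 0.82. With the 36 completers it is 0.33² × 36 × 2 = 7.84 on 1 and 34 df, and power is 0.776. Either way this is power for a difference between groups and says nothing about precision for IBS-S alone.

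**What the Group test can distinguish.** Its noncentrality is δ√(18/2) = 3δ, where δ is the difference between the two mean falls in SD.
- IBS-S falls 0, IBS-No S falls 1.0: δ = 1.0, power 0.83.
- IBS-S falls 0.5, IBS-No S falls 1.5: δ = 1.0, power 0.83.

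The test treats the two cases alike, although IBS-S responds in one and not in the other. This result does not depend on alpha or the SD scale.

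**Precision for the IBS-S change.** The expected 95% CI half-width is t(0.975, 17)/√18 = 2.110/4.243 = 0.497, or about 0.50 SD (0.47 with all 20).

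**Chance that a true IBS-S fall would be non-significant** (paired t test as an illustration, noncentrality d√18, 17 df):

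| True fall (SD of change) | 18 completers | 20 subjects |
|---|---|---|
| 0.33 (plan's 0.33 read as d) | 74% | 71% |
| 0.50 | 48% | 43% |
| 0.66 (plan's 0.33 read as f, d = 2f) | 25% | 20% |

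The 0.5 SD entry is sensitive to the assumptions. At 18 completers it is 35% with a one-sided 0.05 test and about three quarters with two-sided 0.01. If the half SD refers to raw activation, it is 61%, 48% or 27% for a pre-post correlation of 0.3, 0.5 or 0.7.

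**Both results in the same trial** (simulation, 18 per group, true IBS-S fall 0.5 SD):

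| True group difference δ | Group effect significant | Group significant and IBS-S fall non-significant |
|---|---|---|
| 0.33 | 16% | 13% |
| 0.50 | 31% | 24% |
| 0.66 | 49% | 34% |
| 1.0 | 83% | 46% |

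Among trials with a significant Group effect, roughly 55% to 85% also have a non-significant IBS-S fall, although IBS-S truly responded.

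**The case against.** A reader might infer that the plan will call IBS-S refractory because a test within IBS-S fails to reach significance, and that it would do so in nearly half of trials. The documents do not support that. No within-IBS-S test is planned and no rule turns on one. The contrasting branch in Aim 2 also depends on the Group comparison. The miss rates above come from an illustrative test, and the 46% needs a 1.0 SD group difference that appears nowhere in the documents. Tying the difference to the plan's 0.33 gives 13% (read as d) or 34% (read as f).

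The wording is also softer than a claim of zero change. The key sentence is hedged twice, 'refractory' is part of a stated prediction, and the plan allows partial refractoriness. 'Persistent' could mean still abnormal, or still above IBS-No S.

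All of this limits how strongly the point can be put, but the gap remains. The hedges attach to the link with clinical response, while persistence itself is taken as shown. If 'persistent' means still above IBS-No S, equal falls could satisfy it too, because the preliminary study found higher IBS-S activation in several regions without any treatment. An undefined term, a test that does not address it and no interval for the IBS-S change leave the conclusion without direct support.

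**Conclusion.** The point holds in a limited form. A significant Group effect in Aim 2 supports a smaller reduction in IBS-S than in IBS-No S. It does not support unchanged or refractory activation, and a non-significant interaction does not by itself support the hypotheses.

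That conclusion follows from the form of the test and needs none of the assumed figures. The figures show that it matters at this sample size: an IBS-S interval of about ±0.50 SD, a 48% chance that a true 0.5 SD fall is non-significant (74% at 0.33 SD, 25% at 0.66 SD), and a joint pattern in about 13% to 46% of trials. They rest on assumed alpha, sidedness, SD scale and true falls. They are not a forecast of how often the investigator would report refractoriness.

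**What to change.** In Specific Aim 2, Analysis/interpretation, state that:
- each group's mean change in visceral HAPN activation will be reported with its 95% CI;
- a significant Group effect will be concluded as a smaller reduction in IBS-S than in IBS-No S;
- 'persistent' or 'refractory' will be used for IBS-S only if the CI for its change excludes a fall that the investigator has fixed, before analysis, as material. The size is the investigator's choice; 0.5 SD of change is only an example.

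In Sample size calculations, amend the sentence on non-significant interactions so that non-significance alone is not read as support.

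The cost is wording and one interval per group from data already planned. The drawback is that the weaker wording will sometimes be needed even when IBS-S truly does not change. With 18 completers and a 0.5 SD margin, that happens in about 35% of trials with a one-sided 95% bound, or about 48% with a two-sided 95% CI. The plan should therefore say which is meant.

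### Aim 2 names no result that would count against Hypothesis 2, and reads improvement in both groups only as partial refractoriness in IBS-S

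*Combined protocol and SAP*

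**What the plan says.** Hypothesis 2 (section A) states that "IBS-S subjects will demonstrate a persistent pattern of abnormal HAPN visceral activations following desipramine therapy, whereas significant improvements in HAPN visceral activations" are expected in the group without somatization. It is therefore a prediction that the two groups will change by different amounts. In section D, Specific Aim 2, the Analysis/interpretation text sets the matching analysis: "Region of interest two-way ANOVA models will be developed in comparing" the baseline-to-desipramine change, with IBS group as the between-subject factor.

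The first paragraph there says what follows if the prediction is borne out. The second takes up one other outcome, improvement in both groups, and for it raises a single explanation: "should HAPN activations be found to improve in both IBS groups following desipramine therapy, the possibility that HAPN visceral activations are indeed partially refractory". The rider for IBS-S is that "the detected between-group differences (IBS-S vs. IBS-No S) in post-desipramine changes in HAPN activation were smaller than expected, and thus not statistically significant". In that event, it says, "the ANOVA analyses would be likely demonstrate statistical trends between the IBS groups". It then turns to recruitment, where "enrollment of additional subjects would be considered if feasible following power calculations". It closes: "This additional step might lead to findings which allow for rejection of the null hypothesis".

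No change in either group, and greater improvement in IBS-S, are not discussed. Aim 1 is different. Its Analysis/interpretation text names an adverse result (a group difference confined to visceral stimuli) and draws the adverse conclusion (separate system-specific defects in place of one global defect).

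**The concern.** Improvement in both groups with no significant difference in change is what an equal desipramine effect would usually produce, and an equal effect contradicts Hypothesis 2. Yet the plan's only explanation for that pattern keeps refractoriness in IBS-S in play, in a weaker form: persistent abnormality becomes partial refractoriness. With no adverse result named, the main Aim 2 conclusion has no agreed way to say that a differential response was not shown.

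The one thing that might separate partial refractoriness from equal benefit is the expected trend. If a trend is uncommon in both cases, it cannot do that work. This is a question of how the result is read. Whether and how to add subjects afterwards is a separate matter.

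**Working it through.** **Inputs from the plan** (B. Sample size calculations): 20 per group; 10% attrition, that is 2 per group, leaving 18; effect size 0.33; power 0.82 for Group x Treatment. **Assumed, because not stated:** two-sided alpha 0.05; 0.33 read as Cohen's f; correlation between the two scans of 0 for the reproduction; a trend meaning 0.05 ≤ p < 0.10.

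**1. Reproducing the 0.82.** For a two-group by two-time interaction, λ = N·f²·m/(1−ρ) = 40 × 0.33² × 2/(1−0) = 8.71. Noncentral F with 1 and 38 df gives power 0.820, which matches. The match uses 20 analysed per group. With 18, λ = 36 × 0.33² × 2 = 7.84, and power with 1 and 34 df is 0.776.

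**2. How likely is a trend?** To take the plan's power at face value with 18 completers per group, use a t-test on change with 34 df. The noncentrality that gives power 0.82 is 2.96. Scale it by the fraction of the planned difference that is true:

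| True difference, as fraction of planned | Noncentrality | P(p<0.05) | P(0.05≤p<0.10) | Share of non-significant results |
|---|---|---|---|---|
| 1 | 2.96 | 0.820 | 0.075 | 42% |
| 1/2 | 1.48 | 0.301 | 0.123 | 0.123/0.699 = 18% |
| 1/4 | 0.74 | 0.111 | 0.077 | 0.077/0.889 = 9% |
| 0 | 0 | 0.050 | 0.050 | 5% |

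With 20 per group (38 df, noncentrality 2.95) the trend probabilities are the same to within 0.1 percentage points. When the difference is smaller than planned, which is the case the paragraph describes, a trend is the exception.

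**3. Dependence on the threshold.** The plan defines no threshold, and its preliminary Findings describe p = 0.3 as trending. If a trend reaches p = 0.3, the share of non-significant results that show one is 53% at half the planned difference, 35% at a quarter and 26% at zero (0.250/0.950). Trends become more common, but they also become common when there is no difference.

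**4. What a confidence interval could say.** In SDs of change, the 95% half-width for the group difference is t(0.975, df) × √(2/n):
- 18 per group: 2.032 × 0.333 = 0.68.
- 20 per group: 2.024 × 0.316 = 0.64.

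The planned difference depends on the metric of 0.33:
- Power 0.82 at 18 per group implies 2.96/√9 = 0.99 SD.
- The reproduction at 20 per group implies √(2 × 8.71/20) = 0.93 SD.
- Read as f for a simple two-group comparison of change, 0.33 implies 2 × 0.33 = 0.66 SD.

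An observed difference of zero with 18 per group would exclude 0.99 or 0.93 SD but not 0.66 SD. With 20 per group it would just exclude 0.66 SD. A statement that the planned difference is ruled out therefore needs the metric first.

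**The case against.** The strongest reply is that the paragraph claims little. It opens as the converse of the supported case, speaks only of a possibility, and its closing sentence concedes that the null has not been rejected. It also ties the explanation to a trend. Under an identical effect, a trend in the predicted direction occurs in only about 2.5% of trials, or about 12% if a trend reaches p = 0.3, so the plan's own condition would usually fail.

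This stands against a stronger reading that a reader might infer: that almost no result, an identical drug effect included, would count against Hypothesis 2, or that a clear negative would be reported as a positive. The documents do not say so. No change in both groups and a reversed direction are left undiscussed and are not claimed as support. Nor can every non-significant result with both means falling be counted as survival of the hypothesis, because that ignores the trend condition.

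It is also fair that calling a trend unlikely depends on the threshold, and that any interval rule needs one named contrast. The plan has several bilateral regions and two distension pressures. It also describes the primary endpoint as a post-treatment difference while analysing change.

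The reply does not supply what is missing. The plan never says that absence of a trend counts against refractoriness, never mentions equal benefit, and leaves the trend undefined.

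**Conclusion.** The point holds as an omission and a one-sided reading. Aim 2 names no result against Hypothesis 2 and explains improvement in both groups with a non-significant difference only as partial refractoriness. That textual finding rests on no numerical assumption.

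The trend check does not repair it. At p < 0.10 a trend appears in about 12% of trials at half the planned difference and 8% at a quarter, against 5% with none. These figures assume two-sided alpha 0.05, 18 completers per group and scaling to the stated 0.82. A looser threshold makes trends more frequent but also raises their frequency under no difference.

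The change should be made, because it determines what Aim 2 can conclude. The ANOVA on change itself is unaffected.

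**What to change.** Replace the reading in the second paragraph of the Aim 2 Analysis/interpretation text with a rule on the group difference in change (IBS-No S fall minus IBS-S fall) and its 95% confidence interval, for one named primary visceral contrast and region of interest:

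- **Interval excludes zero in the predicted direction:** Hypothesis 2 supported.
- **Interval includes zero, whether both groups improve or neither changes:** Hypothesis 2 not supported, differential response not shown; report the interval.
- **Interval excludes zero in the opposite direction:** evidence against Hypothesis 2.
- **Planned difference ruled out:** state this only if the whole interval lies below that difference, and only after the sample size section gives the metric of the 0.33.

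Delete the clause that trends would be likely, and give a trend no interpretive weight. The enrolment clause in the same sentence needs its own rule.

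The cost is wording plus two decisions, the primary contrast with its region and the effect-size metric. No new data or subjects are needed. The downside for the sponsor is that a non-significant result can no longer be presented as possible partial refractoriness.

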**Specific Aim 2. To compare the effects of antidepressant therapy HAPN activations following noxious visceral stimulation in IBS subjects based on the presence of somatization.**

Rationale: Case-control and randomized clinical trial data have established that somatization predicts symptom responses to IBS therapy with the tricyclic antidepressant desipramine. Specifically, IBS-S subjects are more refractory to antidepressant therapies, while IBS-No S subjects have better overall responses to the same treatment. A recent study has demonstrated improvements in HAPN visceral activations (anterior cingulate cortex) following desipramine therapy in an IBS cohort. Given these observations, the goal of this Aim is to assess whether differences in visceral HAPN activation patterns following desipramine treatment can be detected in IBS-S and IBS-No S subjects.

Design and Methods: The proposed study implements open-label desipramine therapy in 40 IBS (20 IBS-S and 20 age-matched IBS-No S) subjects. Participants from Aim 1 will be invited to continue on to open-label therapy in Aim 2. IBS-S and IBS-No S subjects will receive a 4-week treatment course with the tricyclic antidepressant desipramine (DES), as detailed in section 2.D., below. Subjects will undergo a fMRI protocol with noxious visceral and somatic stimuli as in Aim 1 at baseline, and then immediately following the 4-week desipramine therapy. Subjects will undergo baseline, and post-therapy assessment of psychiatric comorbidity (depression/anxiety) and IBS symptom severity (as described in 3.A. and 3.B., below). The primary endpoint is differences in visceral stimulation-induced brain activations of the HAPN on fMRI, ascertained between-groups following desipramine therapy. The proposed study design is outlined in Figure 9.

[figure not shown]
**Figure 9. Overview of study design for Specific Aim 2.** IBS patients with somatization (IBS-S) and without somatization (IBS-No S) will be identified. A baseline fMRI protocol (as in Aim 1) will be obtained at baseline, followed by a 4-week, open-label treatment with desipramine. A second fMRI protocol will be performed post-desipramine therapy at week 4. The primary endpoint of interest is post-treatment differences in visceral HAPN activations between IBS-S and IBS-No S subjects.

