### Data Analysis and Sample Size Calculations

The proposed experimental include visceral and somatic stimuli which will be studied in a block design, and the obtained functional MRI activations will be analyzed using the general linear model, combined with appropriate corrections for multiple comparisons. These methods are implemented within a set of proprietary display and analysis tools developed by Washington University investigators within the Mallinckrodt Institute of Radiology (MIR). The general linear model will be applied to produce statistical and magnitude maps. All analyses will be done assuming a standard Boynton hemodynamic response curve; this assumption has been valid in previous experiments conducted by [name] which have examined similar brain regions of interest (ROIs) in this protocol. The statistical maps are then used to define activated regions within subjects. Random effects models for group comparisons will be performed in several ways. The increases or decreases in strength of response

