(Delta S/S) will be the metric that is used. To statistically evaluate this, ROI analysis will be conducted in anatomically constrained areas along with voxel-by-voxel analysis. Both ROI-directed and voxel-by-voxel repeated measures ANOVAs (using parameters described below) are done across subjects using model estimates as inputs. Interaction effects and other activations resulting from specific comparisons of a subset of the events will be reported at an uncorrected threshold of  $p < 0.001$  for descriptive purposes. For the insular cortex, prefrontal cortex, orbitofrontal cortex, anterior cingulate cortex, and thalamic nuclei, predetermined ROIs will be used and will include any activations within these regions. A small volume correction will be applied, in keeping with the *a priori* hypotheses regarding these regions. Predetermined ROIs from the HAPN in Talairach space will be drawn using the Talairach atlas coordinate system^99 and the software ANALYZE™ will then be applied to all the participants. Regions which would not be expected to differ between the study populations will also be selected for analysis, and will provide internal activation standards to provide for the specificity of the findings (i.e., control regions). All selected ROIs will be used as a mask to constrain the regions in which test for differences are conducted. These regions will be used as a mask in an overlay on functional datasets to test the

hypotheses. Only areas with significant F-values on the ANOVA and falling within these regions will be used in statistical analyses. There will be 3 event types included in the model, resulting from the combination of all possible stimulus and response conditions: Visceral-Low distention (25-mm Hg), Visceral-High distention (50-mm Hg), and the Somatic stimulus. Voxel-by-voxel analyses will be conducted primarily to ensure that unpredicted differences a priori ROIs which are significant are not overlooked.

[figure not shown]

Figure 13: Study power as a function of sample size and effect.

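### Aim 2 lets a non-significant group comparison prompt further enrolment in the hope of rejecting the null, with no numeric trigger, cap, pooling rule or second-test adjustment; pooling and retesting at the same level would push type I error above nominal

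*Combined protocol and SAP*

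**What the plan says.** The provision is in Specific Aim 2, Analysis/interpretation. It takes the case "should HAPN activations be found to improve in both IBS groups following desipramine therapy", and supposes that the IBS-S versus IBS-No S differences in change "were smaller than expected, and thus not statistically significant". In that event "the ANOVA analyses would be likely demonstrate statistical trends between the IBS groups". The remedy offered for this situation is that "enrollment of additional subjects would be considered if feasible following power calculations". The purpose follows: "This additional step might lead to findings which allow for rejection of the null hypothesis".

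The comparison discussed there is the change from baseline, with IBS group as the between-subject factor. The Aim 2 design text and the Figure 9 caption word the endpoint differently: "The primary endpoint of interest is post-treatment differences in visceral HAPN activations between IBS-S and IBS-No S subjects".

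Under Data Analysis and Sample Size Calculations, the general linear model is "combined with appropriate corrections for multiple comparisons", with a small-volume correction for the predetermined regions. "Both ROI-directed and voxel-by-voxel repeated measures ANOVAs" are planned. Repeated looks at accumating subjects are not mentioned. Section B, Sample size calculations, is built on 20 per group, allows for two lost per group, and describes no interim look or sample-size re-estimation.

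**The concern.** Subjects would be added because the first between-group test failed, with rejection of the same null as the hoped-for outcome. Adding subjects helps to reject that null only if the enlarged data are tested again. If the pooled data are tested at the level already used, the comparison gets a second chance of a false positive that the nominal level does not cover.

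The text does not say whether a trend is required or merely expected, how large it must be, how many subjects may be added, or how the cohorts would be combined. With none of this fixed in advance, the p-value after an extension could not be properly corrected. At stake is the comparison on which the study is powered and on which the claim of desipramine refractoriness in IBS-S rests.

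**Working it through.** **Inputs from the documents.** First analysis at 20 per group (Aim 2 design); extension described when both groups improve and the difference in change is non-significant (Aim 2 analysis text); effect size 0.33 and power 0.82 for Group x Treatment, 10% attrition (section B).

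**Assumptions, because the plan is silent.** Two-sided level 0.05; one two-sample t test on change scores; one extension of 5, 10, 20 or 40 per group; pooled retest at 0.05; trend meaning p<0.10, p<0.20 or any non-significant p.

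**1. The plan's own figure.** The documents give no type I error for the extension, so the only figure to reproduce is the power of 0.82. Section B names a 2-way ANOVA and the Group x Treatment effect. It does not give alpha, the effect-size metric or the pre/post correlation. Take 0.33 as Cohen's f and the two scans as uncorrelated. The standardised difference in change is then d = 2 x 0.33 x √2 = 0.933, and the noncentrality is (20/2) x 0.933² = 8.71. With 38 df and alpha 0.05, power is 0.82, which matches. With 18 completers per group it is 0.78.

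**2. Direction of the error.** Under the null,

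overall error = α + P(not significant first, extended, significant on retest).

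The second term is positive whenever an extension can occur, so the total exceeds α at any nominal level.

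**3. Size under the conditions the plan describes.** Simulation with 4 million trials, equal true change of 0.33 SD in both groups. Extension occurs only if the difference is in the predicted direction, both observed means improve and the trigger is met. The last column sets the added number to give 80% power at the observed difference, limited to 5-40 per group.

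| Trigger | +5 | +10 | +20 | +40 | Power-based |
|---|---|---|---|---|---|
| p<0.10 | 5.35% | 5.31% | 5.26% | 5.20% | 5.23% |
| p<0.20 | 5.63% | 5.66% | 5.62% | 5.52% | 5.55% |
| Any non-significant | 5.73% | 5.99% | 6.30% | 6.58% | 6.61% |

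With no group difference, extension occurs in 1.6%, 5.2% and 42% of studies under the three triggers.

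Sensitivity:
- At a true change of 0.6 SD, with the same fixed additions: 5.32-5.55%, 5.75-5.96% and 6.05-6.92%.
- If each group's improvement must itself be significant (changes up to 0.6 SD): 5.0-5.3% with a trend threshold, up to 5.9% without.
- With 18 per group, the table's figures agree within 0.1 point.

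**4. Size if direction and improvement are ignored.** The two test statistics have correlation √(n₁/(n₁+n₂)); for 20 then 20 added this is √0.5 = 0.707. Integrating the bivariate normal over the extension region gives:

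| Trigger | +5 | +10 | +20 | +40 |
|---|---|---|---|---|
| p<0.10 | 6.07% | 5.97% | 5.82% | 5.64% |
| p<0.20 | 6.79% | 6.89% | 6.76% | 6.49% |
| Any non-significant | 7.09% | 7.70% | 8.31% | 8.83% |

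At nominal 0.01 the same calculation gives 1.4-1.9%, and at 0.001 it gives 0.16-0.19%.

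**5. Levels that restore 5%.** For an equal-weight inverse-normal combination with the same level at both looks, that level is 0.0415 (trigger p<0.10), 0.0352 (p<0.20) or 0.0294 (any non-significant). Using 0.05 at both looks gives 5.8%, 6.8% and 8.3%. At d = 0.933 and 20 per group, first-look power is 0.797, 0.776 and 0.752 at the three adjusted levels, against 0.820 at 0.05.

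**The case against.** The strongest reply is that little is at stake. Extension is only to be considered, subject to feasibility and a power calculation, in one described scenario with trends expected. If a trend is required, the excess is 0.2 to 0.7 points, and without a true group difference an extension would be rare. The study is open-label and mechanistic, with no placebo arm. Pooling and retesting at the same level are nowhere stated. The model is a single test, whereas the plan examines several regions, so the decimals should not be over-read.

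Much of this stands. It limits the size and makes the error statement conditional. It does not remove the gap: the trend is predicted rather than required, a power calculation based on the observed difference does not protect the level (last column of the first table), and the corrections in the analysis section address regions and voxels. The study also names a primary endpoint and speaks of rejecting the null, so the provision cannot be set aside as purely exploratory.

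Three stronger readings are tempting and not supported:
- A reader might infer that there is no trigger at all. There is a qualitative one, plus the feasibility and power-calculation condition; what is missing is a numeric trigger.
- A reader might infer enrolment until significance. Uncapped additions of 10 per group after any non-significant result would give 9.6% after two and 13.9% after five, but the text speaks of one additional step and does not plan repeated ones.
- A reader might infer that an extension would show as an analysed total above 40. Section B's attrition leaves 40 - 4 = 36, so a small extension could stay at or below 40, and ordinary over-enrolment could exceed it.

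**Conclusion.** The point holds in conditional form and should be fixed. The plan allows enrolment to be extended because the Aim 2 comparison of change was non-significant, and does not specify the rule needed to keep the error rate at its nominal level. If the added subjects are pooled and retested at the same level, type I error is above that level whatever the level is.

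The range runs from about 5.2-5.7% on the narrowest reading to 7.1-8.8% when any non-significant result in either direction suffices, with 5.7-6.6% between. These figures rest on the assumed 0.05 level, a single test and a single extension; the first and middle ranges also assume that both groups truly improve by 0.33 SD. Confidence is high about the missing rule and the direction of the error, and lower about its size, which depends on choices that the plan leaves open. The documents do not show that the error will be inflated, because they do not commit to extending or pooling.

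**What to change.** Replace the two extension sentences in the Aim 2 analysis text with a rule such as: *The analysis of the planned 20 subjects per group, with its confidence interval, is the Aim 2 result; any analysis including subjects enrolled later will be labelled exploratory or reported as a separate replication cohort.* State whether this covers the comparison of change, the post-treatment comparison in the design text and Figure 9, or both.

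A replication cohort should be reported beside the planned result, not in its place. If a rejection in either cohort counted as success, the error would be 0.05 + (L - 0.05) x 0.05 for trigger p<L: 5.25% for L = 0.10, 5.75% for 0.20 and 9.75% for any non-significant result.

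If a pooled extension is kept as confirmatory, prespecify one extension, a numeric trigger, a cap, and a combination test with stage weights and adjusted levels fixed in advance. The levels in step 5 of the working are examples. They ignore the direction and improvement conditions, so they are conservative if those also apply.

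The cost is wording only. Under the first option, a trend can no longer be rescued as a confirmatory result. Under the second, first-look power falls from 0.82 to roughly 0.75-0.80, before any gain from the extension, assuming f = 0.33, alpha 0.05 and uncorrelated pre/post scans.
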